16.2. LABORATORY EVALUATIONS

The specific hematology, chemistry, and urinalysis analytes collected for the study are described in Appendix 2 of the protocol. Summary tables and listings of local laboratory data will be represented in SI units, where applicable. Laboratory values that are reported as 'below the detectable limit' of an assay will be analyzed as half the detectable limit for quantitative analysis but listed as originally reported. The following summaries will be provided for laboratory data:

- Shift from baseline grade to worst post-baseline grade based on NCI CTCAE v5.0 (for analytes where CTCAE grading applies). A missing baseline grade will be assumed to be grade 0. For laboratory tests with both low and high values, summaries will be provided separately.
- Shift from baseline to worst post-baseline value that is $< 0.25 \times LLN$ or $> 2.5 \times ULN$ (for analytes not gradable by NCI CTCAE v5.0).

All lab data will be listed. An additional listing will be presented for subjects with a post-baseline analyte that is grade 3 or higher (per NCI CTCAE) or that is $< 0.25 \times LLN$ or $> 2.5 \times ULN$ (for analytes not gradable by NCI CTCAE). For the later listing, all values for that analyte will be listed.

16.3. PERFORMANCE STATUS ANALYSIS

ECOG performance status score will be summarized and listed for the Enrolled population. ECOG performance status will be summarized categorically at baseline, best post-baseline value, and worst post-baseline value. A summary of shift from baseline (improved, no change, deteriorated) will be performed for the best post-baseline value and the worst post-baseline value during the study. Best and worst post-baseline values will be flagged in the listing.

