13. STATISTICS

Summaries of continuous variables will present the number of subjects included in the analysis (N), the mean and standard deviation (SD), the median, the minimum, and the maximum statistics. Counts and percentages will be presented in summaries of categorical variables. The denominator for each percentage will be the number of subjects in the population unless otherwise specified. In general, missing data will not be imputed unless otherwise specified.

All disposition, baseline demographics and disease characteristics will be descriptively summarized for the Safety population

Analyses will be done separately for each study part and overall.

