13.3. Safety analyses

Safety analyses will be based on all subjects who receive at least 1 dose or partial dose of study drugs (Safety population). Drug exposure will be summarized using descriptive statistics. The severity of all adverse events is to be evaluated by the Investigator based on the National Cancer Institute (NCI) Common Terminology Criteria for Adverse Events (CTCAE) version 5.0 and verbatim terms will be coded to the preferred term (PT), higher level term (HLT), and system organ class (SOC) using the Medical Dictionary for Regulatory Activities (MedDRA) version in use at the time of the analysis. The number and percentage of subjects with adverse events will be presented by MedDRA SOC and PT, relationship to study treatment, and severity. Clinical laboratory values also will be classified by toxicity grade based on the NCI CTCAE, version 5.0. Laboratory shift tables from baseline result to the worst post-baseline result will be provided. AEs will be summarized separately for: AEs, serious AEs, AEs leading to discontinuation, AEs leading to death, Grade 3, or higher AEs (per NCI CTCAE Version 5.0). Physical examination, vital signs, 12-lead ECG, and ECOG performance status will be descriptively summarized based on marked abnormality criteria.

Analyses will be done separately for each study part and overall.

Complete details of the safety analysis will be provided in the statistical analysis plan (SAP).

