2. STUDY OBJECTIVES AND ENDPOINTS

2.1. PRIMARY AND SECONDARY OBJECTIVES AND ENDPOINTS

Objectives	Endpoints
Part 1: Tazemetostat and Itraconazole	
Primary: 
 To evaluate the effect of CYP3A4 inhibition by itraconazole on the steady-state pharmacokinetics (PK) of tazemetostat when administered as a single and twice daily oral dose in subjects with advanced malignancies 	
 AUC_{0-t}: area under the plasma concentration-time curve from time 0 to the time of the last quantifiable concentration AUC_{0-72}: area under the plasma concentration-time curve from time 0 to 72 hours post-dose C_{max}: observed maximum plasma concentration
Secondary: 
 To evaluate the steady-state safety profile of tazemetostat when co-administered as a single and twice daily oral dose with itraconazole in subjects with advanced malignancies 	
 Safety parameters: Adverse event assessment, physical examination, vital signs (blood pressure, heart rate, body temperature), 12-lead ECG, clinical laboratory tests (hematology including coagulation profile, serum chemistries, urinalysis), ECOG performance status, and concomitant medication monitoring

 To evaluate the steady-state PK of tazemetostat and its metabolites after administration alone and with itraconazole To evaluate the effect of itraconazole on PK of a single 400 mg oral dose of tazemetostat. 	
 AUC_{0-t}: area under the plasma concentration-time curve from time 0 to the time of the last quantifiable concentration C_{max}: observed maximum plasma concentration T_{max}: observed time at C_{max} λ_z: terminal phase elimination rate constant $t_{1/2}$: terminal elimination half-life
Part 2: Tazemetostat and Rifampin	
Primary: 
 To evaluate the effect of CYP3A4 induction by rifampin on the steady-state PK of tazemetostat when administered as a single and twice daily oral dose in subjects with advanced malignancies 	
 AUC_{0-t}: area under the plasma concentration-time curve from time 0 to the time of the last quantifiable concentration AUC_{0-48}: area under the plasma concentration-time curve from time 0 to 48 hours post-dose

[figure not shown]
Objectives	Endpoints
	
 • C_{max}: observed maximum plasma concentration

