6.2.2. BASELINE ASSESSMENTS

Baseline data are defined as the last non-missing assessment (including unscheduled assessments) prior to starting treatment. If there is more than one value on or prior to starting treatment, the value closest to and prior to the receipt of the first dose, whether scheduled or unscheduled, will be used as the baseline value. Unless the collection time or label indicates otherwise, assessments performed on the same day as the first dose of study drug will be considered performed prior to the start of treatment. AEs and medications reported with a start date on the date of first dose will be considered to have occurred after the start of treatment. For vital signs (excluding weight and height) and ECG measures, baseline results will be identified for the set.

For laboratory parameters, the baseline time point will be determined separately for each parameter.

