11. DEMOGRAPHIC AND OTHER BASELINE CHARACTERISTICS

Demographic data and other baseline characteristics will be summarized by study part and overall, and listed for the Enrolled population. Demographics will include age (derived, in years), sex, race, ethnicity, and baseline characteristics will include, but not limited to, Eastern Cooperative Oncology Group (ECOG) performance status, complete physical examination, vital signs and drug/alcohol screening details.

Baseline disease characteristics will include tumor diagnosis (TD), prior anticancer therapy (yes/no), prior radiotherapy (yes/no), prior cancer related surgery (yes/no), progressive disease prior to study entry (yes/no), prior disease progression date of last progression prior to the study enrollment, blood smear (BS), Bone Marrow Aspirate/Biopsy (BM) and time from date of last disease progression to study entry (in months).

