16. SAFETY OUTCOMES AND ANALYSIS

All safety summaries will be based on the Safety population.

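### SAP 16.3 puts the ECOG post-baseline and shift summaries on the Enrolled population, against the SAP's own safety rule, and the SAP moves the baseline tables to Enrolled without declaring the change from the protocol

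*SAP*

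**What the plan says.** **ECOG.** SAP 16.3: "ECOG performance status score will be summarized and listed for the Enrolled population". The same paragraph asks for baseline, best post-baseline and worst post-baseline categories, and for shifts classed as improved, unchanged or deteriorated.

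**The general safety rule.** SAP 16, of which 16.3 is a subsection: "All safety summaries will be based on the Safety population". It gives no exception. SAP 5 assigns the Enrolled population to demographic and baseline disease summaries, and the Safety population to safety and tolerability.

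**ECOG as a safety measure.** The safety parameters in SAP 2.1 include "clinical laboratory tests (hematology including coagulation profile, serum chemistries, urinalysis), ECOG performance status, and concomitant medication monitoring". Protocol 13.3 bases the safety analyses on subjects who received at least a partial dose, and within that section says: "Physical examination, vital signs, 12-lead ECG, and ECOG performance status will be descriptively summarized based on marked abnormality criteria".

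**Baseline tables.** Protocol 13: "All disposition, baseline demographics and disease characteristics will be descriptively summarized for the Safety population". SAP 11: "Demographic data and other baseline characteristics will be summarized by study part and overall, and listed for the Enrolled population". SAP 3.2, which lists changes from the protocol, has three items. None concerns an analysis population.

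**Definitions.** SAP 5 defines Enrolled by consent and meeting the screening criteria. Safety is the subset of Enrolled with at least a partial dose and at least one post-dose safety observation.

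**The concern.** A programmer cannot follow both SAP 16 and SAP 16.3. If 16.3 is followed, an enrolled subject who never took study drug can count in the denominator of a post-baseline shift table without being able to contribute to any shift category. The percentage deteriorated could then be understated, and ECOG deterioration and adverse-event incidence would have different denominators in one report.

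The baseline tables raise a different issue. Summarising baseline data on all enrolled subjects is a legitimate choice, but it is not the one the protocol makes, and the section meant to record such departures does not mention it.

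**Working it through.** **1. Do the texts conflict?**

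| Output | One source | Another source |
|---|---|---|
| ECOG post-baseline values and shifts | Safety (SAP 16; SAP 5 and 2.1 read together; Protocol 13.3) | Enrolled (SAP 16.3) |
| Demographics, disease characteristics | Safety (Protocol 13) | Enrolled (SAP 5, SAP 11) |

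The first row is a contradiction within the SAP and with the protocol. The second is a departure from the protocol that SAP 3.2 does not declare.

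**2. Can Enrolled exceed Safety?** Yes, in principle. A subject may meet the criteria and withdraw before the first dose, or take a dose and have no post-dose safety observation. Let k be the number of such subjects. The documents give no value for k.

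**3. Which denominator applies?** SAP 6.3 takes percentages over the named analysis population unless otherwise specified, and SAP 16.3 specifies nothing else. SAP 7 allows a category for missing values, which would show the gap but leave these subjects in the denominator.

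**4. Effect on a shift percentage.** None of the k subjects can have a post-baseline ECOG. Never-dosed subjects have no post-baseline period. For a dosed subject, a post-dose ECOG would itself be a safety observation and would bring that subject into Safety. So the numerator d is the same on either population:

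- Enrolled: d/N
- Safety: d/(N−k)
- Ratio: (N−k)/N

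**5. Numbers.** Planned enrolment reproduces: 24/(1−0.40) = 40, or 12/(1−0.40) = 20 per part. The even split between parts is an assumption. Taking N = 20 and, for illustration, d = 4:

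| k (assumed) | Factor | Enrolled | Safety |
|---|---|---|---|
| 0 | 1.00 | 4/20 = 20.0% | 4/20 = 20.0% |
| 1 | 19/20 = 0.95 | 20.0% | 4/19 = 21.1% |
| 2 | 18/20 = 0.90 | 20.0% | 4/18 = 22.2% |
| 3 | 17/20 = 0.85 | 20.0% | 4/17 = 23.5% |

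The 40% dropout allowance is not a never-dosed rate and is not used as k.

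**6. Does changing the population settle the denominator?** Not fully. In Protocol Tables 3 and 4, the first scheduled ECOG after day −1 is on day 15. A subject dosed on day 1 who leaves before day 15, and has no ECOG at the end-of-study visit, can be in the Safety population with no post-baseline value. If m is the number of such subjects, the percentage among those with data is d/(N−k−m). With k = 0 and an assumed m = 2, that is 4/18 = 22.2% against 4/20 = 20.0%. The documents do not give m either.

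**The case against.** The strongest reply is that the gap may be empty. Protocol 7.3 gives a subject number only after all selection criteria are met, Tables 3 and 4 recheck eligibility on day −1, and it is reconfirmed before the first dose. A subject who fails a recheck may not count as Enrolled at all. If every enrolled subject is dosed and observed, the two populations coincide and no figure changes. This stands: dilution is a possible consequence of the rule, not an established one. It does not remove the conflict in the text.

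Stronger readings are tempting, and the documents do not support them:

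- A reader might infer that the baseline table describes different people from the adverse-event and PK tables. It does not. SAP 5 makes Safety a subset of Enrolled and PK a subset of Safety, so every subject in those tables is in the baseline table, possibly with a few more. SAP 8 also reports the population counts and lists each subject's membership.
- A reader might infer that Protocol 13 also requires the Safety population for surgical and medical history (SAP 12). Protocol 13 does not name it. Prior anticancer therapy (SAP 13.1) is covered only if read as a disease characteristic, as SAP 11 treats it.
- A reader might see a clash between the Enrolled population and the baseline rule in SAP 6.2.2: "Baseline data are defined as the last non-missing assessment (including unscheduled assessments) prior to starting treatment". For a never-dosed subject that rule is silent rather than contradictory, and screening values can still be tabulated.

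**Conclusion.** Both discrepancies hold, as a minor correction. SAP 16.3 names a population that its parent section, SAP 5 and Protocol 13.3 do not allow for a safety summary. SAP 5 and 11 depart from Protocol 13 for the baseline tables without saying so.

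The size is conditional. The ECOG shift percentages are multiplied by (N−k)/N, with k unknown and possibly zero; 0.95 to 0.85 corresponds to an assumed k of 1 to 3 among an assumed 20 per part, under the SAP 6.3 default denominator. Counts do not change.

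The stakes are low. The ECOG summaries are descriptive, no test uses them, SAP 16 keeps the other safety summaries on the Safety population, and the PK primary analysis is untouched.

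**What to change.** 1. In SAP 16.3, replace Enrolled with Safety. State that shift percentages are computed among Safety subjects with a baseline and at least one post-baseline ECOG, and show the number without one. The population change alone would leave early leavers in the denominator.
2. For demographics and disease characteristics (SAP 5 and 11), either present the tables on the Safety population as in Protocol 13, keeping Enrolled as a supplement if wanted, or keep Enrolled and declare the change in SAP 3.2.

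The cost is a few words in the SAP, a population flag and a denominator condition in the table programs. No data collection changes. SAP 1 requires the plan to be final before database lock, so the edit belongs before then.

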16.4. ECG EVALUATIONS

12-Lead echocardiogram (ECG) measures (singlets and triplicates) will be collected according to the schedule of events, which varies by study part. When triplicates are collected, the averages will be used in the summaries.

The investigator will provide an overall interpretation of the ECG (i.e. clinically significant, yes or no). For the Fridericia correction of QT interval for heart rate (QTcF), markedly abnormal criteria will be defined as described in the table below.

ECG values, the investigator's interpretation of the ECG, and other information collected will be listed. QTcF values meeting markedly abnormal criteria will be flagged.

The following tables will be provided for the QTcF:

- Quantitative 12-lead ECG measurements: Shift from baseline to worst post-baseline in QTcF status categorized as markedly abnormal or not (defined in the table below)
- Quantitative 12-lead ECG QTcF measurements: Counts and percentages of subjects whose worst-case changes from baseline in QTcF measurements meet markedly abnormal criteria (described in the table below for changes from baseline).

QTcF Measure	Markedly Abnormal Criteria
Observed Measures	450–480 msec, inclusive [CTCAE grade 1] 481–500 msec, inclusive [CTCAE grade 2] > 500 msec [CTCAE grade 3 or higher]
Observed Changes from Baseline	>30 msec increase from baseline >60 msec increase from baseline

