13. Females of childbearing potential (FCBP) must either practice complete abstinence or agree to use a highly effective method of contraception beginning at least 28 days prior to the first dose of study drug, during study treatment (including during dose interruptions), and for 6 months after study drug discontinuation. If the below contraception methods are not appropriate for the FCBP, she must be referred to a qualified contraception provider to determine the medically effective contraception method appropriate for the subject. The following are examples of highly effective methods of contraception (result in a failure rate of <1% per year when used consistently and correctly):
 - Intrauterine device (IUD)
 - Intrauterine hormone-releasing system (IUS)

- Hormonal (ovulation inhibitory combined [estrogen and progesterone]: oral, intravaginal, or transdermal; ovulation inhibitory progesterone-only: oral, injectable, or implantable)

NOTE: Due to the potential of enzyme induction with tazemetostat, hormonal contraception methods must be supplemented with a barrier method of contraception (preferably male condom)

- Bilateral tubal ligation
- Partner's vasectomy (if medically confirmed [azoospermia] and sole sexual partner)

NOTE: Female subjects of childbearing potential exempt from these contraception requirements are subjects who practice complete abstinence from heterosexual sexual contact. True abstinence is acceptable when this is in line with the preferred and usual lifestyle of the subject. Periodic abstinence (eg, calendar, ovulation, symptothermal, or post-ovulation methods) and withdrawal are not acceptable methods of contraception.

14. Male subjects must have had a successful vasectomy (with medically confirmed azoospermia) OR must either practice complete abstinence or agree to use a latex or synthetic condom during sexual contact with a female of childbearing potential (FCBP) from the first dose of study drug, during study treatment (including during dose interruptions), and for 3 months after study drug discontinuation.

NOTE: Male subjects must not donate sperm from the first dose of study drug, during study treatment (including during dose interruptions), and for 3 months after study drug discontinuation.

15. Has a QT interval corrected by Fridericia's formula (QTcF) ≤ 450 msec.
16. Subjects with diagnosed human immunodeficiency virus (HIV) are eligible to participate in the study if they meet the following criteria:

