12.3.4. Electrocardiogram (ECG)

A standard 12 lead ECG will be performed. ECG collection will occur after a 10-minute rest and with the subject in a supine position. ECGs will be collected prior to any blood sample collection, including PK samples.

The ECGs will be performed as indicated in the Schedule of Assessments and Procedures (Table 3 and Table 4). A single ECG will be recorded unless there is an abnormality, such as prolonged QT interval corrected for heart rate using Fridericia's formula (QTcF) >450 msec, new arrhythmia, or other clinically significant findings. If an abnormality is observed, the ECG is to be performed in triplicate at least 2 minutes apart. Machine read ECGs should be reviewed by the Investigator at the time of assessment. ECGs will be read locally within 72 business hours and data entered in the clinical database. See Table 9 for timing window allowances. On days when an ECG assessment and a PK blood sample collection are scheduled at the same time (see Table 3 and Table 4), the ECG assessment should be performed immediately prior to collection of the PK blood sample, if possible.

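### The QTcF shift table in SAP 16.4 collapses three graded bands into yes/no, so it cannot show who went above 500 msec; the band limits also need tidying

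*SAP*

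**What the plan says.** SAP 16.4 (ECG Evaluations) plans two QTcF tables. The first is "Shift from baseline to worst post-baseline in QTcF status categorized as markedly abnormal or not (defined in the table below". The second counts subjects whose worst-case increase from baseline exceeds 30 or 60 msec. All ECG values are to be listed, with values that meet the criteria flagged.

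The observed-value criteria are three bands, each carrying a grade label: "450–480 msec, inclusive [CTCAE grade 1", then "481–500 msec, inclusive [CTCAE grade 2", then "> 500 msec [CTCAE grade 3 or higher".

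On repeated recordings, SAP 16.4 says: "When triplicates are collected, the averages will be used in the summaries". It gives no rule for rounding an average before it is classified.

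The protocol uses 450 msec in two places. Section 8.1, criterion 15, admits subjects with "QTcF) ≤ 450 msec". Section 12.3.4 calls for triplicate recordings when an abnormality is seen, and its examples are "QTcF) >450 msec, new arrhythmia, or other clinically significant findings".

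For gradable laboratory tests, SAP 16.2 plans a shift from baseline grade to worst post-baseline grade.

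**The concern.** The SAP sets out three bands of increasing severity and then tabulates shifts on a two-state version of them, with no reason given. A two-state table cannot separate a trivial crossing of the lowest bound from a rise above 500 msec, and it cannot show worsening in anyone who starts inside the lowest band.

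ECG is a named safety endpoint in both parts. Protocol 5.3 expects CYP3A4 inhibition to raise tazemetostat exposure, and the Part 1 schedule takes ECGs before dosing and 2 hours after tazemetostat on several co-administration days. With 12 completers planned per part, one completer is 1/12 = 8.3% of that group, so a single subject above 500 msec should be visible in a table.

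The bands are also not quite usable as written. The first ends at 480 and the second starts at 481, while averages of triplicates need not be whole numbers. The lower bound includes 450, a value that the protocol accepts at entry.

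**Working it through.** The plan gives no figure to reproduce. The check is to apply the SAP's bands literally.

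**Inputs.** Bands and table wording from SAP 16.4; baseline definition from SAP 6.2.2; eligibility limit from Protocol 8.1; triplicate trigger from Protocol 12.3.4. The baseline and worst values below are illustrations.

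**Step 1: the two-state table.** Let M(x) = yes if 450 ≤ x ≤ 480, or 481 ≤ x ≤ 500, or x > 500; otherwise M(x) = no. The shift table shows only M(baseline) and M(worst).

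| Baseline → worst (msec) | Shift table shows | By SAP band | Change | >30 | >60 |
|---|---|---|---|---|---|
| 449 → 451 | no → yes | none → grade 1 | +2 | no | no |
| 449 → 501 | no → yes | none → grade 3 or higher | +52 | yes | no |
| 450 → 480 | yes → yes | grade 1 → grade 1 | +30 | no | no |
| 450 → 501 | yes → yes | grade 1 → grade 3 or higher | +51 | yes | no |
| 450 → 511 | yes → yes | grade 1 → grade 3 or higher | +61 | yes | yes |
| 475 → 502 | yes → yes | grade 1 → grade 3 or higher | +27 | no | no |

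Rows 1 and 2 share a cell. Rows 3 to 6 share another, and it reads as no shift.

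**Step 2: what the change table recovers.** If the worst value w exceeds 500, then w − baseline > 500 − baseline.

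- From a baseline of 450 or less, the rise exceeds 500 − 450 = 50 msec, so it always counts under >30. It is certain to count under >60 only if the baseline is 440 or less.
- From a baseline above 470, the rise can be 30 msec or less and be missed, as in row 6.
- The >30 row does not identify values above 500: 400 → 440 (+40) is counted there too.

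**Step 3: can baseline exceed 450?** SAP 6.2.2 takes the last value before treatment. Protocol Tables 3 and 4 schedule ECGs at screening and before dosing on day 1, but not on day -1, where the second eligibility check is marked. The protocol also says that eligibility is reconfirmed before day 1 dosing, without saying whether the day 1 ECG is part of that. A baseline above 450 is therefore possible, not certain. If the day 1 ECG is used to exclude such subjects, only a baseline of exactly 450 is masked.

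**Step 4: the gap.** Assume readings in whole msec (the documents do not state the precision). A triplicate mean is S/3, where S is the sum.

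| S | Mean (msec) | SAP band |
|---|---|---|
| 1440 | 480 | grade 1 |
| 1441 (e.g. 479, 480, 482) | 480.33 | none |
| 1442 (e.g. 479, 481, 482) | 480.67 | none |
| 1443 | 481 | grade 2 |

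Read literally, 480.33 is not markedly abnormal although 480 and 481 both are. The decimal-place rule in SAP 7 governs how means are displayed; it does not round a value before classification.

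**Step 5: exactly 450.** M(450) = yes. Under Protocol 8.1 the value 450 is eligible, and it lies outside the >450 example in Protocol 12.3.4. Within the eligibility limit this is the only value on which the documents differ.

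**The case against.** The strongest reply is that a value above 500 would not go unseen. A rise from 450 or less to above 500 always enters the >30 msec row. Every ECG value is listed and those meeting the criteria are flagged, which is manageable for about 40 subjects. Protocol 12.4.1.4 has worsening or clinically significant ECG findings recorded as adverse events, and SAP 16.1 tabulates grade 3 or 4 events. This stands, and it rules out a stronger reading that one might infer, namely that progression above 500 msec would be lost from the report. But each route is partial. The change table does not identify the level reached, the listing is not a count, and the adverse event route depends on what the investigator records.

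A second reply is that the wording may be loose. It points to a table of graded bands, the laboratory section shifts by grade, and the table shells are not in the documents. That is possible, but the text says abnormal or not, and a programmer would follow it.

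Third, the 450 mismatch is small. One might infer that the SAP labels a range of protocol-normal values as abnormal, or that the protocol defines only values above 450 as abnormal. Neither is supported. A single value is affected, and the protocol gives >450 as an example that triggers repeat ECGs, not as an analysis definition. The SAP also ties its lower bound to a CTCAE label, so there may be a reason to keep it.

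Fourth, the 480–481 gap is narrow. Non-integer triplicate means are common, and one might infer that many values would be unclassified. Only means strictly between 480 and 481 are, and that matters only where such a value is the one classified.

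**Conclusion.** The concern holds as a defect of display in a descriptive safety analysis. The one planned table of observed QTcF discards the SAP's own grading. It cannot separate 451 from above 500, it hides any worsening from a baseline of 450 or above, and it leaves no ECG table that counts subjects above 500 msec. The other planned outputs soften this but do not replace such a count.

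The band limits are a lesser matter: two possible means between 480 and 481 if readings are in whole msec, and one value, 450, to reconcile. How many subjects will be affected cannot be estimated from the documents.

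The conclusion rests on reading the shift table as two-state, which is what the text says. If the shells already shift by grade, only the wording and the band limits remain. The primary PK endpoints are untouched.

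**What to change.** In SAP 16.4, replace the yes/no table with a shift table of baseline category by worst post-baseline category, using four levels: normal, grade 1, grade 2, and above 500 msec. State that the categories apply to the averaged value, and make them contiguous by defining the second band as >480 to 500. Values of 480.33 and 480.67 then fall in that band, 450 → 501 appears as a move to the top category, and 449 → 451 and 449 → 501 fall in different cells.

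Reconcile exactly 450 msec between the SAP band and the protocol threshold. Either start the first band at >450, or keep 450 in it with its CTCAE label and say that the analysis category differs from the protocol's threshold on purpose. This concerns the analysis categories only and does not touch eligibility or ECG procedures.

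The cost is SAP wording and one table shell. No new data are needed, and the result matches the by-grade shift that SAP 16.2 already uses for laboratory data.
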